5.6.1.2. Pembrolizumab

- Number of cycles received by patient
- Number of patients treated by cycle
- Duration of treatment (in weeks) = $[(\text{Date of last dose} - \text{date of first dose}) + 21] \div 7$
- Cumulative dose (mg) = Sum of all doses administered
- Dose intensity (mg/week) = (Cumulative dose) \div (Duration of treatment)
- Relative dose intensity (%) = Dose intensity (mg/week) \div (200 mg / 3 weeks)
- Dose delay as recorded on the CRF.

The relative dose intensity will be additionally presented categorized (that is, number and percentage of patients with relative dose intensity of $< 60\%$, $\geq 60\%$ - $< 80\%$, $\geq 80\%$ - $< 90\%$, $\geq 90\%$ - $< 110\%$, $\geq 110\%$).

Moreover, the number and percentage of patients with any dose delay, with any dose reduction (reduction to first or second dose level) will be presented as well as the number (%) of patients with infusion interrupted.

5.6.2. Adverse Events

Adverse events will be summarized by MedDRA™ System Organ Class (SOC) and preferred term (PT), classified from verbatim terms. The incidence and percentage of patients with at least one occurrence of a PT will be included, according to the most severe National Cancer Institute Common Terminology Criteria for Adverse Events (NCI-CTCAE) Version 4.0 grade.

If more than one AE is recorded for a patient within any PT the patient will only be counted once on the most severe grade. Missing classifications concerning study treatment relationship will be considered as related to study treatment.

A treatment-emergent adverse event (TEAE) is defined as an event that first occurred or worsened between the first dose of study treatment and 30 days after the last dose of study treatment and related serious AEs (SAEs) reported beyond 30 days after the last dose of study treatment.

5.6.2.1. Overall Summary of Adverse Events

An overall summary of AEs will be provided to summarize the following categories using frequency counts and percentages:

- patients with at least one TEAE, SAE,
- deaths
- subjects who discontinued study treatment due to AE
- TEAE related to study treatment

5.6.2.2. Treatment-Emergent Adverse Events (TEAEs)

The following summaries of TEAEs will be provided (*repeat for events deemed by the investigator to be possibly related to study medication):

- by PT*
- by SOC and PT, and by maximum CTCAE grade *

A patient listing of all AEs will be provided.

5.6.2.3. Adverse Event of Special Interest

Adverse events of special interest (AESI) include events related to arterial thromboembolism (ATE), venous thromboembolism (VTE), skin reactions (rash will be identified separately), conjunctivitis, hypersensitivity/infusion related reaction (IRR), hypomagnesemia, and interstitial lung disease (pneumonitis). Each AESI is defined by a set of MedDRA PTs and the PT lists were identified by the medical and safety physician for the compound based on the (blinded) review of all PTs (without looking at the number of patients/events for that PT) reported. The final list of AESI categories will be reported in the CSR.

The incidence of treatment-emergent AESI will be summarized by AESI category and PT.

5.6.2.3.1. Thromboembolic Adverse Events

Thromboembolic AEs according to the AESI criteria outlined above are classified as arterial thromboembolic AE and venous thromboembolic AE. Treatment emergent thromboembolic SAEs will be tabulated by overall, arterial thromboembolic AE and venous thromboembolic AE. A listing of all treatment emergent thromboembolic adverse events will be generated.

In order to further assess the thromboembolic adverse events observed in the study, an additional analysis examining possible risk factors for such events will be performed. Identification of these risk factors will be based on a literature search (Scappaticci et al. 2007; Khorana et al. 2008; Choueiri et al. 2010; Hurwitz et al. 2011; Petrelli et al. 2012; Lyman et al. 2013).

5.6.2.4. Events of Clinical Interest (ECIs) - Pembrolizumab

The 2 categories of events of clinical interests (ECIs) for pembrolizumab include:

1. an overdose of pembrolizumab (≥ 1000 mg [5 times the dose]) not associated with clinical symptoms or abnormal laboratory results, and
2. an elevated AST or ALT lab value that is greater than or equal to 3X the upper limit of normal (ULN) and an elevated total bilirubin lab value that is greater than or equal to 2X ULN and, at the same time, an alkaline phosphatase lab value that is less than 2X ULN, as determined by way of protocol-specified laboratory testing or unscheduled laboratory testing. Please refer to the Site Guidance Document for Drug-induced Liver Injury.

The treatment emergent ECIs will be summarized and listed separately.

5.6.2.5. Consolidated Adverse Event

Consolidated AE categories include Anemia, Fatigue, Hypercalcaemia, Hyperkalaemia, Hypermagnesaemia, Hyponatraemia, Hyperphosphataemia, Hypocalcaemia, Hypokalaemia, Hypomagnesaemia, Hyponatraemia, Hypophosphataemia, Leukopenia, Neutropenia and Thrombocytopenia. Each category contains PTs identified as clinically identical or synonymous and PT lists were identified by the medical and safety physician for the compound based on the (blinded) review of all PTs (without looking at the number of patients/events for that PT) reported. The final list of consolidated AE categories will be reported in the CSR.

The incidence of treatment-emergent consolidated AEs will be summarized by consolidated category and PT.

5.6.3. Deaths, SAEs, and Other Significant AEs

Reasons for deaths (study disease, AE [any AE, study treatment related AE], etc.) will be summarized separately for 1) all deaths, 2) death on therapy, 3) deaths within 30 days discontinuation of study therapy, 4) deaths on therapy or within 30 days of discontinuation of study therapy and 5) deaths after 30 days of discontinuation of study therapy.

Serious adverse events will be summarized by SOC and PT, by maximum CTCAE grade and by SOC and PT, and repeated for events deemed by the investigator to be possibly related to study medication. A listing of SAEs will be produced.

In addition, the following analyses will be performed:

- Listing of AEs leading to death
- Listing of AEs leading to study treatment discontinuations
- AEs leading to study treatment dose modification by SOC and PT

Dose-limiting toxicity (DLT) will be listed for Part A only.

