Objectives: The primary objectives of the study are: Part A: to determine the dose-limiting toxicity (DLT) of necitumumab at doses of 600 mg and 800 mg on Days 1 and 8 when combined with pembrolizumab 200 mg on Day 1 every 3 weeks (Q3W), in patients with Stage IV NSCLC as measured by the number of patients with a DLT in Cycle 1. Part B: to evaluate the efficacy of necitumumab in combination with pembrolizumab in terms of overall response rate (ORR) by Response Evaluation Criteria in Solid Tumors Version 1.1 (RECIST 1.1) in patients with Stage IV NSCLC. Part C: to determine the DLT of necitumumab at the recommended dose from Part A in combination with pembrolizumab in Japanese patients with Stage IV NSCLC as measured by the number of patients with a DLT in Cycle 1. The secondary objectives of the study are: Part A and Part C: 
 to investigate the safety profile as assessed by clinical and laboratory significant events of necitumumab in combination with pembrolizumab to determine the ORR by RECIST 1.1 to determine the pharmacokinetics (PK) of necitumumab in presence of pembrolizumab to determine the immunogenicity of necitumumab in presence of pembrolizumab Part B: to demonstrate the feasibility of necitumumab at the recommended dose in combination with pembrolizumab by: 
 investigating the safety profile as assessed by clinical and laboratory significant events determining disease control rate (DCR), duration of response (DOR), progression-free survival (PFS), and overall survival (OS) by RECIST 1.1. determining PK of necitumumab in presence of pembrolizumab determining the immunogenicity of necitumumab in presence of pembrolizumab The exploratory objective is to further evaluate as follows:	

Parts A, B, and C: to investigate relationship between immune- and EGFR-pathway-related biomarkers and treatment outcomes.

Part B: to assess immune-related (ir)ORR, irDCR, irDOR, and irPFS by adapted RECIST 1.1 (immune-related RECIST [irRECIST]).

Study Design: This is an open-label, multicenter Phase 1b study with an expansion cohort to investigate necitumumab in combination with pembrolizumab in approximately 78 patients with Stage IV NSCLC (American Joint Committee on Cancer Staging Manual, 7th edition). The study consists of 3 parts:

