
Criteria for Evaluation: Efficacy: Objective Response Rate (ORR) is defined as the proportion of patients achieving a best overall response of partial response (PR) or complete response (CR). Disease Control Rate (DCR) is defined as the proportion of patients achieving a best overall response of stable disease (SD), PR, or CR. Progression-Free Survival (PFS) is defined as the time from the date of first dose of any study drug until the date of radiographically documented PD or death due to any cause, whichever is earlier. Overall Survival (OS) is defined as the time from the date of first dose of any study drug to the date of death from any cause. Safety: Part A and Part C: DLTs, serious adverse events (SAEs), adverse events (AEs), vital sign measurements, laboratory analyses, and electrocardiograms (ECGs) Part B: SAEs, AEs, vital sign measurements, laboratory analyses, and ECGs Pharmacokinetics: Serum concentrations of necitumumab prior to infusion (minimum concentration [C_{min}]) and at end of the necitumumab infusion (approximately maximum concentrations for necitumumab). Bioanalytical: Serum concentrations of necitumumab will be measured using validated enzyme-linked immunosorbent assays. Immunogenicity: Serum anti-necitumumab antibody titer levels will be determined. Translational research: A tumor tissue block or tumor tissue slides will be collected to correlate biomarker results with clinical outcomes related to the EGFR pathway, innate and adaptive immunity, and/or other biomarkers associated with the disease pathobiology and therapeutic molecules. Blood samples will be collected for exploratory biomarker analyses.

Statistical Methods:

Efficacy: The primary Part B outcome variable in this study will be the ORR. The Part B statistical null hypothesis states that the true ORR is 20%, whereas the research hypothesis states that the true ORR is 35%. If the research hypothesis is true, there is an 83% chance of rejecting the null hypothesis. If the null hypothesis is true, then there is at most a 10% chance of rejecting the null hypothesis. Therefore, the sample size of 54 evaluable patients in Part B has a nominal one-sided alpha level of 0.10, with statistical power of 83%.

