9.4.1. Special Treatment Considerations

9.4.1.1. Dose-Limiting Toxicity (Parts A and C)

A DLT is defined as one of the following AEs, occurring in Cycle 1 if considered to be definitely, probably, or possibly related to necitumumab and pembrolizumab. The following list will define DLT:

- Grade 3 or 4 nonhematologic toxicity according to the NCI-CTCAE Version 4.0, except for skin toxicity, nausea, vomiting, diarrhea, or electrolyte disturbance (see below). For patients with \leq Grade 2 hepatic transaminase levels at baseline as a result of liver metastases, a transaminase level ≥ 10 x ULN lasting for >7 days will be considered a DLT.
- Grade 4 nausea, vomiting, or diarrhea that persists more than 3 days despite maximal supportive intervention
- Grade 3 thrombocytopenia with bleeding requiring transfusion
- Grade 4 thrombocytopenia with or without bleeding
- Grade 4 neutropenia that persists more than 5 days
- Grade 3 or 4 neutropenia with fever, defined as single temperature of $>38.3^{\circ}\text{C}$ (101°F) or a sustained temperature of $\geq 38^{\circ}\text{C}$ (100.4°F) for more than one hour
- Grade ≥ 3 skin toxicity despite best supportive care, with exception of Grade 3 rash that resolves to Grade ≤ 2 within 14 days with appropriate supportive therapy
- If a total at least 75% of the planned dose for both agents cannot be administered in the first cycle due to toxicity
- Prolonged delay (>2 weeks) in initiating cycle 2 due to treatment-related toxicity
- Grade 5 toxicity

DLT is defined by sponsor and principal investigator.

The following toxicities will not be considered DLTs if they are transient (<7 days):

- Hypersensitivity and injection site reactions (If a Grade 3 or 4 hypersensitivity/IRR to necitumumab or pembrolizumab occurs, this event will not be considered a DLT; the patient will not receive any further study therapy and will be replaced in the study by a new patient.)
- Grade ≥ 3 myalgia, fatigue, or constipation, with full supportive therapy
- Grade ≥ 3 increase or decrease of electrolytes
- Grade 3 nausea, vomiting, or diarrhea that resolves to Grade ≤ 1 within 7 days of appropriate supportive therapy
- Grade ≥ 3 elevation of serum creatine kinase level that is asymptomatic that returns to Grade ≤ 2 within 21 days of necitumumab treatment interruption

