Changes from Statistical Analysis Plan Version 1.0

1. Part C has been added according to the protocol JFCQ(a)
2. The timing of Primary analysis and final analysis for Parts A and B have been updated according to the protocol JFCQ(a)
3. Events of Clinical Interest (ECIs) have been updated according to the protocol JFCQ(a)
4. Interim efficacy analyses have been added according to the protocol JFCQ(a)
5. Various sections modified according to the new TAFFY standard TFL shells

Changes from Statistical Analysis Plan Version 2.0

1. The final analysis has been removed per protocol update
2. Interim efficacy analyses for squamous patients has been added

4. Study Objectives

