4.1. Primary Objective

This study is divided into 3 parts:

Part A: to investigate safety and tolerability of pembrolizumab 200 mg Q3W when combined with necitumumab administered at the doses of 600 mg and 800 mg on Days 1 and 8 of 21-day cycles in patients with Stage IV NSCLC (all histologies) as measured by number of patients with a dose-limiting toxicity (DLT) during Cycle 1.

Part B: to evaluate the efficacy of necitumumab in combination with pembrolizumab in terms of overall response rate (ORR) by Response Evaluation Criteria in Solid Tumors Version 1.1 (RECIST 1.1) in patients with Stage IV NSCLC of squamous and nonsquamous histology.

Part C: to investigate safety and tolerability of pembrolizumab 200 mg Q3W when combined with necitumumab administered at the recommended dose from Part A in Japanese patients with Stage IV NSCLC of squamous and nonsquamous histology as measured by number of patients with a DLT during Cycle 1.

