5.1. Determination of Sample Size

A total of approximately 78 patients for either Part A, Part B or Part C will be enrolled. Part A requires up to 12 treated patients (3-6 for Cohort 1 and 6 for Cohort 2). Patients with squamous and nonsquamous NSCLC from Part A who received the recommended necitumumab dose for Part B will also be analyzed together with Part B. In Part C, approximately 6-12 Japanese patients will be enrolled and treated with necitumumab at the recommended dose from Part A in combination with pembrolizumab.

The primary analysis of the Part A and Part B will take place approximately 6 months after the last patient evaluable for Part B portion of the study has been enrolled. The primary Part B outcome variable in this study will be ORR. The Part B statistical null hypothesis states that the true ORR associated with the regimen of necitumumab and pembrolizumab is 20%, whereas the research hypothesis states that the true ORR associated with the combination regimen is 35%.

If the research hypothesis of a 35% ORR is true, there is an 83% chance of rejecting the null hypothesis. If the null hypothesis of a 20% ORR is true, then there is at most a 10% chance of rejecting the null hypothesis. Therefore, the sample size of 54 evaluable patients in Part B has a nominal one-sided alpha level of 0.10, with statistical power of 83%.

The analysis of Part C will take place approximately after all the patients from Part C have completed 8 cycles or discontinued early. At the same time, some of the efficacy of part B may be updated, where appropriate.

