5.5.5. Primary Efficacy Endpoint

The primary endpoint for Part B is ORR. The denominator of ORR includes all evaluable patients, and the numerator includes those patients counted in the denominator with a best overall tumor response of partial or complete response (PR or CR) per RECIST 1.1.

Confirmation of objective response is required for this trial. To be assigned a best overall response status of PR/CR, changes in tumor measurements must be confirmed by repeat assessments that should be performed no less than 4 weeks after the criteria for response are first met. In this circumstance, the best overall response can be interpreted as in [Table JFCQ.5.1](#). In the case of stable disease (SD), measurements must have met the SD criteria at least once after first dose at a minimum interval of 6 weeks. Patients' responses after objective progression or start of new anticancer therapy are excluded from the determination of best response.

The primary analysis for ORR is a one-sided exact binomial test with the null hypothesis of 20% at a 10% significance level. For Part B evaluable patients, the p-value from this test will be presented. The ORR and its 95% confidence intervals (CIs) will be estimated.

Table JFCQ.5.1. Best Overall Response when Confirmation of CR and PR Required

Overall Response First Time point	Overall Response Subsequent Time point	BEST Overall Response
CR	CR	CR
CR	PR	SD, PD or PR ^a
CR	SD	SD provided minimum criteria for SD duration are met. Otherwise PD
CR	PD	SD provided minimum criteria for SD duration are met. Otherwise PD
CR	NE	SD provided minimum criteria for SD duration are met. Otherwise NE
PR	CR	PR
PR	PR	PR
PR	SD	SD
PR	PD	SD provided minimum criteria for SD duration are met. Otherwise PD
PR	NE	SD provided minimum criteria for SD duration are met. Otherwise NE
NE	NE	NE

Abbreviations: CR = complete response; NE = inevaluable; PD = progressive disease; PR = partial response; SD = stable disease.

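### The SAP lists dose-limiting toxicities for Part A only, so the Part C primary endpoint, the number of Japanese patients with a Cycle 1 DLT, has no planned output

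*SAP*

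**What the plan says.** SAP section 4.1 states the Part C primary objective as safety and tolerability "in Japanese patients with Stage IV NSCLC of squamous and nonsquamous histology as measured by number of patients with a DLT during Cycle 1". Protocol section 6.1 agrees, and the protocol synopsis sets the objective "in Japanese patients with Stage IV NSCLC as measured by the number of patients with a DLT in Cycle 1".

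The protocol carries DLTs through to Part C in three further places:
- The synopsis safety criteria read "Part A and Part C: DLTs, serious adverse events (SAEs), adverse events (AEs), vital sign measurements".
- The heading of section 9.4.1.1 applies the DLT definition to Parts A and C.
- Section 8.1 makes 2 patients with DLTs among the first 6 in Part C the trigger for sponsor review.

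On output, SAP section 5.6.3 says "Dose-limiting toxicity (DLT) will be listed for Part A only". For Part C, SAP section 5.1 gives the sample size (6 to 12 patients) and the timing: "The analysis of Part C will take place approximately after all the patients from Part C have completed 8 cycles or discontinued early". SAP section 5.2 adds that Part C will be reported apart from the other parts, without naming any output.

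**The concern.** A SAP should name at least one output that delivers each primary endpoint. Here the only sentence about DLT output excludes the part whose primary endpoint is a DLT count. This goes beyond silence: a programmer following section 5.6.3 literally would omit Part C, and the SAP would then fail its own section 4.1. At stake is whether the Part C primary result is reported as a prespecified analysis or has to be added outside the SAP, with its content decided after the data are seen.

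**Working it through.** The documents give no figure for this point, so the check is a reading of the text. The Part B power calculation has no bearing on it.

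**1. Where the SAP mentions DLTs.** There are two places: the objectives (4.1) and the output sentence (5.6.3). None of the exposure, adverse-event, laboratory, subgroup or interim sections mentions them.

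**2. Primary measure against named output, by part.**

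| Part | Primary measure (SAP 4.1) | Output named in the SAP |
|---|---|---|
| A | Patients with a Cycle 1 DLT | DLT listing (5.6.3) |
| B | ORR by RECIST 1.1 | One-sided exact binomial test, p-value, ORR with 95% CI (5.5.5) |
| C | Patients with a Cycle 1 DLT | None; excluded from the DLT listing (5.6.3) |

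For Part B the SAP is explicit: "For Part B evaluable patients, the p-value from this test will be presented". Part A has a listing and no stated count, but with at most 12 patients the count can be read straight from it. Part C has neither. So 3 − 1 = 2 of the 3 part-specific primary endpoints have an output, and 1 has none.

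**3. Whether the protocol fills the gap.** Section 12.2.6, on the primary outcome, covers only ORR and its intervals. Section 12.2.10, on safety analyses, covers exposure, adverse events, deaths, hospitalizations and transfusions, but not DLTs.

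**4. Whether other SAP outputs give the count indirectly.** Part C patients would appear in:
- the adverse-event and SAE tables and listings;
- the listing of events leading to discontinuation;
- the dose-modification summary;
- the exposure and dose-delay data (5.6.1 to 5.6.3).

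None of these is planned to carry a DLT flag, and the dose outputs are not planned by cycle in a form that isolates Cycle 1 delivery. Protocol section 9.4.1.1 lists 10 DLT criteria. Two are not adverse-event grades: failure to deliver at least 75% of planned dose because of toxicity, and a toxicity-related delay of more than 2 weeks in starting Cycle 2. That leaves 10 − 2 = 8 based on grades. Several of those also depend on duration, supportive care or attribution, and the section goes on to exempt certain transient events. It adds "DLT is defined by sponsor and principal investigator", which can be read as making DLT status a judgement on each case. On either reading, the general outputs do not reliably yield the count.

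**5. How the sentence may have arisen.** The SAP revision history shows that Part C entered in the changes from Version 1.0, and the sentence still stands after the changes from Version 2.0. A missed update is a plausible explanation, but it is an inference and the conclusion does not rely on it.

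**The case against.** The strongest reply concerns weight. Part C has 6 to 12 patients, no hypothesis test and no power claim, and protocol section 8.2 describes the outcome as hypothesis-generating. The sponsor must know the Part C DLT count during the study to apply the 2-of-6 rule. Protocol section 12.2.1 lets the SAP make only minor changes or clarifications, so the SAP cannot remove a protocol endpoint. All of that stands, and it confines the consequence to reporting. It does not reconcile section 5.6.3 with section 4.1: an in-study decision is not a prespecified analysis, and the endpoint's survival in the protocol is why the SAP has to deliver it.

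A second reply is that section 5.6.3 restricts only what is listed, and the general line in section 5.2 about reporting Part C separately could cover a DLT summary. That line says how Part C is grouped and names no DLT output, so the specific restriction governs.

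A third is that crediting Part A with an output is generous, since its measure is also a count and it receives only a listing. This is fair, and the fix adds the count for Part A as well. The distinction remains that the Part A listing gives the answer directly, while Part C is excluded.

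Finally, much could be traced by hand for so few patients. The tally of two ungraded criteria counts bullets; the first bullet also contains a transaminase rule stated in multiples of the upper limit of normal. The sentence about who defines a DLT may refer to authorship of the definition. These points soften the claim that the count cannot be rebuilt, but they do not supply a planned output.

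**Conclusion.** The concern holds. As written, the SAP contradicts its own primary objective: one of three part-specific primary endpoints has no planned DLT output, and the sole DLT sentence excludes it. It should be corrected before the Part C analysis because it concerns a primary endpoint. The practical effect is nevertheless limited to prespecified reporting of a count over at most 12 patients. No estimate, error rate, safety oversight step or Part B conclusion changes. The finding rests on the text of the two documents and on no numerical assumption.

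A related detail is also unsettled, though the finding does not depend on it. Protocol section 8.1 describes the DLT population under Part A and does not repeat it for Part C. Section 9.4.1.1, which covers both parts, contributes only a replacement rule for severe hypersensitivity or infusion reactions. SAP section 5.2 defines no DLT-evaluable population.

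**What to change.** Replace the DLT sentence in SAP section 5.6.3 with wording such as: *DLTs will be listed, and the number of patients with at least one Cycle 1 DLT will be reported, for Part A by cohort and for Part C.* The cost is one sentence, one added listing and a simple count over at most 12 Part C patients, plus the matching Part A count. No new data are needed.

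Separately, protocol sections 8.1 and 9.4.1.1 and SAP section 5.2 should be reconciled so that both documents agree on who is DLT-evaluable in Part C. This needs a short protocol clarification that the SAP then mirrors; the SAP should not choose the rule on its own.
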